The non-vitamin K oral anticoagulants (NOACs) are a new group of drugs which have been recently approved for use as blood thinners. They have a faster onset of action compared to warfarin and unlike warfarin, they do not need frequent monitoring. Apixaban and Rivaroxaban both have a similar mechanism of action. They inhibit Factor 10 which a clotting factor. They are the most commonly prescribed NOACs at Einstein Medical Center Philadelphia. We intend to serially monitor the kidney function by measuring the serum creatinine and urinalysis of 40 high risk patients who are recently started on either apixaban or rivaroxaban over a six month period. This will enable us to discover what proportion of patients actually develop ARN after starting a NOAC.

2) Project Objectives and Hypotheses:

Determine the incidence of ARN in high risk patients on rivaroxaban or apixaban (Factor 10 inhibitors).

Hypothesis - the incidence of ARN with apixaban or rivaroxaban is less than the previously reported incidence of ARN in warfarin.

- Describe demographic and urinalysis-associated predictors of ARN in patients on rivaroxaban or apixaban (Factor 10 inhibitors)

3) Background/Significance of Research (*Provide the scientific or scholarly background and rationale for the research based on the existing literature (include references). Describe relevant prior experience and gaps in current knowledge. Describe any relevant preliminary data. Explain the significance of the research in terms of why it's important and how it will add to existing knowledge.*):

Anticoagulation-related nephropathy (ARN) is an understudied renal complication of anticoagulant therapy that is characterized by acute kidney injury (AKI) defined as an increase in baseline serum creatinine ≥ 0.3 mg/dL, without any alternate etiology, in the setting of a supra-therapeutic International Normalized Ratio (INR) greater than 3.0 [1-7]. ARN has mainly been studied in relation to warfarin, it usually occurs in the first two months of starting anticoagulant therapy and retrospective studies have estimated the prevalence to range from 16% to 37% [4-6]. The strongest risk factor for ARN is pre-existing chronic kidney disease (CKD); other risk factors include older age, diabetes mellitus and hypertension [1,4]. Patients with ARN have an accelerated progression of CKD and a retrospective study of more than 15,000 patients on warfarin showed a 65% increase in mortality in patients with ARN [4,6].

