Secondary endpoint - Urinalysis measurements (particularly hematuria and proteinuria) will be analyzed for correlation with the incidence of ARN. Demographic variables including age and race will be analyzed in contingency tables using Fisher's exact test to ascertain if they are significant for the primary outcome.

- ii. Describe any primary or secondary safety endpoints (*e.g. any disease or symptom that would result in the withdrawal of that subject from the study*): Subjects will be censored from the study if anticoagulation is withdrawn for any clinical reason

e. Human Research Methods:

- i. Describe and explain the study design (*e.g. randomized, double-blind, placebo-controlled clinical trial or retrospective chart review*):

This is a prospective observational study designed to determine the incidence of ARN in 40 adult patients recently initiated on rivaroxaban or apixaban at Einstein Medical Center Philadelphia.

- ii. Describe all research activities involved in this protocol, including a study visit timeline if appropriate:

Baseline demographic data, past medical history, current medication list and baseline laboratory records (taken within the last three months) will be obtained from the patient's hospital chart and the electronic medical record. Serum creatinine and urinalysis measurements will then be repeated at monthly intervals for the first three months and then at the six-month mark. These laboratory tests will be drawn at Einstein's Klein building Suite 100 by a trained phlebotomist.

If AKI, defined as an increase in baseline serum creatinine ≥ 0.3 mg/dL from baseline, is noted in any study participant, the patient and his primary care physician or cardiologist will be notified both verbally and through a detailed letter. A standard clinical evaluation and work up will then be performed by the patient's primary care physician or cardiologist as part of the patient's usual care with referral to a nephrologist if necessary. The research team will then be notified of the result of this work up.

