- i. Describe steps that will be taken to secure the data (e.g. training, authorization of access, password protection, encryption, physical controls, certificates of confidentiality and separation of identifiers and data) during storage, use and transmission: As stated above, a study participant list containing identifiable data will be password protected and stored on the Einstein system. This list will only be able to be accessed by members of the research team. All other data will be stored in a separate database with unique but unidentifiable identification numbers. At the termination of the study the initial study participant list will be deleted.
- ii. Describe the data analysis plan, including any statistical procedures and method for determining the sample size for the study:

Incidence of ARN is the primary outcome of this study and this is based on a documentation of AKI (defined as an increase in baseline serum creatinine ≥ 0.3 mg/dL), in the absence of any other obvious etiology for the AKI identified after a standard clinical evaluation and work up by the patient's primary care physician, cardiologist or nephrologist. This incidence will be expressed as a percentage.

Urinalysis measurements (particularly hematuria and proteinuria) will be analyzed for correlation with the incidence of ARN. Demographic variables including age and race will be analyzed in contingency tables using Fisher's exact test to ascertain if they are significant for the primary outcome.

There is no data at all in the literature for the incidence of ARN with rivaroxaban or apixaban and we short-listed that number (40) based on the reported incidence for warfarin (17-37%). We are selecting the patients at highest risk (elderly, CKD) for anticoagulation-related nephropathy (ARN) and we expect that the incidence we obtain will be the highest for the population we are studying.

In terms of precision, we will calculate confidence intervals of the proportional incidence using Stata (command line `cii 40 (incidence)`). If the incidence is zero, Stata calculates the 95% confidence interval based on our sample size as 0-9%. If we only find 2 cases of ARN, Stata calculates the point estimate incidence at 5% with 95% confidence interval as 0.6% - 17%, If we find 10 cases of ARN, Stata calculates the point estimate incidence as 25% with 95%

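### Age is recorded as a number but must be grouped for Fisher's exact test at an unstated cut, which loses power by an amount that depends on the cut

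*Protocol*

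**What the plan says.** The second objective in section 2 (Project Objectives and Hypotheses) is to "Describe demographic and urinalysis-associated predictors of ARN in patients on rivaroxaban or apixaban". The method appears under Study Design, part d (Study Endpoints, secondary endpoint), and is repeated in part g (Data Management), item ii: "Demographic variables including age and race will be analyzed in contingency tables using Fisher's exact test". The stated purpose is a significance test, "using Fisher's exact test to ascertain if they are significant for the primary outcome". No age groups, cut-point or other analysis of age are given.

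Part e (Human Research Methods), item vii, lists age among the baseline variables, and item ii says birth dates are held on the participant list, so exact age is available. The study is "designed to determine the incidence of ARN in 40 adult patients". The background section names older age as an ARN risk factor, and the inclusion criteria restrict entry to patients aged 60 or over.

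**The concern.** A contingency table needs categories. Putting age into one means choosing a cut and then treating all patients on the same side of it as equal. With 40 patients and few events, Fisher's test is also coarse: only a handful of p-values are possible, and at some cuts none falls below 0.05. Age is named explicitly, so this is a stated method rather than a detail left open.

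At stake is the reading of a secondary result. A non-significant table could be taken as evidence that age does not matter when the test had little power at the chosen cut. With no cut fixed, a significant table could reflect a cut picked because it worked.

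**Working it through.** **Inputs from the protocol.** N = 40. The worked scenarios in the data analysis plan are 0, 2 and 10 cases. N was chosen with a warfarin incidence of 17–37% in mind: 0.17 × 40 = 6.8 and 0.37 × 40 = 14.8, so about 7 to 15 cases. The hypothesis is that "the incidence of ARN with apixaban or rivaroxaban is less than the previously reported incidence of ARN in warfarin", which points to fewer.

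**Assumptions, not in the protocol.** Two-sided 0.05 level; normally distributed age; cases older by 1 SD unless stated; the age splits shown below.

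**The plan's own figures.** Exact (Clopper–Pearson) 95% limits for 0, 2 and 10 cases of 40 are 0–8.8%, 0.6–16.9% and 12.7–41.2%. These agree with the stated 0–9%, 0.6–17% and 13–41%. They concern incidence only; no power is stated for the predictor analysis.

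**Smallest attainable p.** At a 20/20 split, the most extreme table has all k cases in one half, so the minimum two-sided Fisher p is 2 × C(20,k)/C(40,k). For k = 2 this is 2 × 190/780 = 0.487. For the exact rank test the minimum is 2/C(40,k), which for k = 2 is 2/780 = 0.0026. At an uneven split, with m patients in the older group, the smallest p is C(m,k)/C(40,k) for the small case counts shown. For m = 8, k = 2 this is 28/780 = 0.036.

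| Cases | Fisher 20/20 | Fisher oldest 10 v 30 | Fisher oldest 8 v 32 | Rank test |
|---|---|---|---|---|
| 2 | 0.487 | 0.058 | 0.036 | 0.0026 |
| 3 | 0.231 | 0.012 | 0.006 | 0.0002 |
| 4 | 0.106 | 0.002 | 0.0008 | 0.00002 |
| 5 | 0.047 | 0.0004 | 0.0001 | 0.000003 |

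At a median split, significance is impossible with 4 or fewer cases, which includes the protocol's 2-case scenario. At an 8/32 split it is possible with 2.

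**Power at a 1 SD shift** (simulation, at least 10,000 runs per setting).

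| Cases | Fisher 20/20 | Fisher, a more favourable cut | Exact rank test |
|---|---|---|---|
| 2 | 0% | 28–29% (8/32) | 22% |
| 4 | 0% | 44% (10/30) | 41% |
| 5 | 34% | 50% (8/32) | 49% |
| 7 | 19% | 50% (13/27) | 61% |
| 10 | 28% | 58% (12/28) | 73% |
| 15 | 67% | 71% (13/27) | 83% |

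Tertiles give 44%, 56% and 66% with 7, 10 and 15 cases. In that range the rank test beat every grouping tried. With 2 to 5 cases some upper-tail cuts match it or do slightly better. The favourable cut also changes with the case count, which is unknown in advance: the 10/30 split gives 44% with 4 cases but 28% with 7.

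**Choosing the cut after seeing the data.** With no age effect, taking the smallest Fisher p over all splits from 4/36 to 36/4 gives a false-positive rate of about 20% with 4 or 7 cases and 22–24% with 10 or 15. The rank test stays at about 5%.

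**Smaller age difference.** At a 0.5 SD shift the rank test itself has only about 20%, 25% and 31% power with 7, 10 and 15 cases.

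**The case against.** The strongest reply is that the largest gaps come from the median split, a cut the protocol never states. That stands. A reader might infer that Fisher's test cannot be significant at all until there are 5 cases; this is true only at 20/20, and an 8/32 or 10/30 split refutes it. A reader might also infer that a null finding on age is close to certain. The documents do not support that either: the protocol works through 10 cases and sized the study around 7 to 15, where power is reduced but not absent.

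The 1 SD difference is also an assumption, and entry at 60 or over may narrow the contrast. With 2 cases, or a 0.5 SD difference, the rank test is weak too. The main limit on this analysis is N = 40, chosen for the precision of an incidence, and a change of test does not remove it.

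Third, a cut-point is commonly left to an analysis plan, which is not at hand, so its absence alone is not a defect. That is fair. But an analysis plan could only supply groups; analysing age as a number would depart from the protocol's own sentence. Last, the point covers age among the demographic variables. The Fisher sentence does not extend to laboratory values such as baseline creatinine.

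**Conclusion.** The point holds in a limited form. The protocol fixes a categorical test for a variable recorded as a number, and this loses information on one of its own risk factors. In the 7-to-15-case range behind the sample size, at a 1 SD shift and two-sided 0.05, a median split costs roughly 42, 45 and 16 percentage points of power with 7, 10 and 15 cases (61 − 19, 73 − 28, 83 − 67). More favourable cuts cost about 11 to 15 points. With 2 to 5 cases the cut decides everything: it may make significance impossible or may equal the rank test.

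The firm conclusion is therefore not that the stated test must fail, but that its performance rests on an arbitrary choice that a rank or continuous analysis avoids. This is worth correcting because it is free, but it concerns a secondary, largely descriptive aim. The incidence estimate and its confidence interval are untouched.

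**What to change.** In both places where the sentence appears (Study Design, part d, secondary endpoint, and part g, item ii), state that age will be analysed as a continuous variable with an exact Wilcoxon rank-sum test. Alternatively, use exact or Firth logistic regression, reporting an odds ratio per 10 years with its 95% confidence interval. Keep Fisher's exact test for categorical demographics such as race and sex.

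The cost is one sentence, changed in two places. It needs no new data, visits or patients. The change will not make the age analysis well powered, so the report should give the estimate and its interval rather than rely on a significance statement.

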Screening will be also be carried out by a query on the electronic medical record with a confidential report generated weekly by the Einstein's AECIS which will contain all rivaroxaban and apixaban prescriptions ordered by electronic scripts. Investigators and co-investigators will review the medical records of patients on the list to determine if they meet the inclusion criteria for the study.

Identified patients will be given a written description about the study and [name] (principal investigator) will be notified. All identified patients will have their medical records/chart reviewed by [name] to determine eligibility for the study. If appropriate, he will then contact them by phone and arrange a meeting to discuss the study protocol, answer any questions and complete the consent process

- ii. Describe the criteria that define who will be included or excluded in your final study sample:

Inclusion Criteria

- Age \geq 60 years
- GFR \leq 90 ml/L based on creatinine clearance
- Participant has been initiated on long term anticoagulation with rivaroxaban or apixaban for atrial fibrillation within four weeks of recruitment
- Participant is willing to comply with all aspects of the protocol, including adherence to medical therapy and follow-up visit
- Participant is willing to give written informed consent

Exclusion Criteria

- History of blood dyscrasias or active bleeding,
- History of hematuria
- Patients on dialysis

c. Study Timelines:

- i. Duration of an individual subject's participation in the study: 6 months
- ii. Time period anticipated to enroll all study subjects or to complete chart review: 4 months
- iii. Estimated overall study duration (*i.e. from initiation to completion of primary analyses*): 12 months

d. Study Endpoints:

- i. Describe the primary and secondary study endpoints (*i.e. the outcome(s) that the study is designed to evaluate*):

Primary endpoint - Incidence of ARN is the primary outcome of this study and this is based on a documentation of AKI (defined as an increase in baseline serum creatinine \geq 0.3 mg/dL), in the absence of any other obvious etiology for the AKI identified after a standard clinical evaluation and work up by the patient's primary care physician, cardiologist or nephrologist. This incidence will be expressed as a percentage.

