- v. Describe alternative treatments that are available to subjects if they choose not to participate in research: No new treatment is started in this study. Patients will be observed in on-going treatment that is started before the observation. Patients who do not participate will continue to receive standard clinical care.

- vi. Describe the source records that will be used to collect data: AECIS records for background demographic data. Laboratory results from the Einstein laboratory after serum creatinine and urinalysis are assayed.

- vii. Describe what data (variables) will be collected for this research: Baseline demographic data (age, sex, height, weight, race), past medical history, current medication list and baseline laboratory records (basic metabolic panel, serum creatinine, urinalysis) will be obtained from the patient's hospital chart and the electronic medical record. Serum creatinine and urinalysis measurements will then be repeated at monthly intervals for the first three months and then at the six-month mark.

- viii. Describe any plans to conduct audio or video recording of research participants during the conduct of the research. Specify whether recording is optional or not and how information on how recordings will be used and how long they will be retained is being shared with subject: N/A

f. Specimen Management:

- i. Will any type of specimen (e.g. blood or tissue) be collected for this study?
 Yes
 No, skip to section on Data Management
- ii. What information will be associated with the specimens collected for this study? Each sample will be labeled with the patient's unique identification number.
- iii. If specimens will be banked for future use, describe where and how the specimens will be stored:
 N/A

- iv. Specify how long specimens will be stored locally: N/A
- v. Specify who will have access to the specimens locally: N/A
- vi. Will specimens be sent out or received: No Yes
 - a. Who is responsible for receipt or transmission of the specimens? N/A
 - b. How will specimens be transported? N/A
 - c. Describe the procedures to release specimens, including: the process to request a release, approvals required for release, who can obtain specimens, and the data to be provided with specimens: N/A

g. Data Management

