- ii. Describe the procedures that will be followed when subjects withdraw from the research (or request that their data be withdrawn), including partial withdrawal from procedures with continued data collection: If a patient is censored from the study, all of their data will be removed from the study participant list and study database.

7) Risks to Subjects:

- a) List the reasonably foreseeable risks, discomforts, hazards or inconveniences to the subjects. For each indicate the probability, magnitude, and duration when possible (consider physical, psychological, social, legal and economic risks as well as risks related to confidentiality): This research has no additional risk above and beyond that of a blood draw and urine collection. Blood draws may rarely cause pain, bleeding and bruising. Blood draws for serum creatinine assay will be performed by a trained phlebotomist using standard techniques.
- b) If applicable, indicate which procedures may have risks to the subjects that are currently unforeseeable: None
- c) If applicable, indicate which procedures may have risks to an embryo or fetus should the subject or the subject's partner be or become pregnant: None
- d) Describe, if applicable, the process that will be followed if a subject or the subjects' partner becomes pregnant while participating in the study: None
- e) If applicable, describe risks to others who are not subjects: None

8) Potential Benefits to Subjects

- a) Describe the benefits that individual subjects may experience (include when possible the probability, magnitude and duration of the potential benefits) or indicate if there is no direct benefit: If a patient develops ARN, this study ensures that the condition will be detected and the patient will receive a comprehensive work up in standard care. The benefit to the patient is that they are receiving extra monitoring for this condition.

9) Medical care and compensation for injury (Required for Greater than Minimal Risk Studies Only):

- a) Describe any provisions for medical care and available compensation in the event of a research related injury: N/A
- b) Provide the contract language, if any, relevant to compensation for research-related injury: N/A

10) Cost to participants:

- a) Describe any actual or potential cost that subjects may incur through participation: There are no costs that the subject may incur.

11) Provisions to Protect the Privacy Interests of Subjects:

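### The censoring rule is tied to withdrawal of anticoagulation in general, not of rivaroxaban or apixaban, so a switch of anticoagulant is handled badly on either reading

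*Protocol*

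**What the plan says.** Section 2 (Project Objectives and Hypotheses) sets the aim: "Determine the incidence of ARN in high risk patients on rivaroxaban or apixaban (Factor 10 inhibitors". The hypothesis is that "the incidence of ARN with apixaban or rivaroxaban is less than the previously reported incidence of ARN in warfarin".

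Under Study Design, the safety-endpoint item of Study Endpoints and the first item of Withdrawal of Subjects give the same rule: "Subjects will be censored from the study if anticoagulation is withdrawn for any clinical reason". The second item of Withdrawal of Subjects states the consequence: "If a patient is censored from the study, all of their data will be removed from the study participant list and study database".

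The drugs are named in the inclusion criteria: "Participant has been initiated on long term anticoagulation with rivaroxaban or apixaban for atrial fibrillation within four weeks of recruitment". The primary endpoint (Study Endpoints, repeated under Data Management) is a creatinine rise of at least 0.3 mg/dL over baseline for which the treating physicians' work-up finds no other obvious cause. It does not require the participant to be on rivaroxaban or apixaban when the rise is found.

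Under Human Research Methods, the medication list is collected with the baseline data. For follow-up, the section says: "Serum creatinine and urinalysis measurements will then be repeated at monthly intervals for the first three months and then at the six-month mark".

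**The concern.** The objective is defined by exposure to two named drugs, while the exit rule is defined by exposure to any anticoagulant. A participant changed to warfarin, dabigatran or a heparin has left the first definition but, on the plain words, not the second.

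The hypothesis compares these drugs with warfarin, so cases arising on warfarin would contaminate exactly that contrast. Section 3 says that ARN usually appears in the first two months of anticoagulant therapy. A switch within the six months could therefore place a participant in the early period on the new drug while still under observation. Treatment is usual care, so the study does not control who switches.

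Switchers who remain event-free are also affected: they would stay in the denominator as though exposed to the study drug for the full six months. With 40 participants and possibly very few cases, one or two events carry much of the result.

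**Working it through.** **1. The Protocol's own figures.** Data Management gives exact 95% intervals for N = 40. For x cases out of n, the Clopper-Pearson limits are the 0.025 quantile of Beta(x, n−x+1) and the 0.975 quantile of Beta(x+1, n−x). For x = 0 the upper limit is 1 − 0.025^(1/n).

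| Cases | Recomputed | Stated |
|---|---|---|
| 0/40 | 0 to 8.8% | 0 to 9% |
| 2/40 | 0.6 to 16.9% | 0.6 to 17% |
| 10/40 | 12.7 to 41.2% | 13 to 41% |

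All three reproduce after rounding. They do not depend on the censoring wording and serve only as the scale for what follows.

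**2. Literal reading: the switcher stays in.** Anticoagulation continues, so the rule does not apply. The endpoint does not ask which drug the participant is taking, so a later qualifying creatinine rise may be counted. The effect of misattributed cases is:

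- 0 true cases plus 1: 1/40 = 2.5% (0.1 to 13.2%), against 0% (0 to 8.8%).
- 0 true cases plus 2: 2/40 = 5.0% (0.6 to 16.9%), which is the Protocol's own two-case scenario.
- 2 true cases plus 1: 3/40 = 7.5% (1.6 to 20.4%), against 5.0% (0.6 to 16.9%).

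The bias is upward, against the hypothesis.

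How many such cases to expect depends on a switch rate that the Protocol does not give. Assume that k of 40 switch to warfarin and that each then carries the Section 3 warfarin range of 16% to 37%. Expected cases are k × p:

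- k = 2: 0.32 to 0.74 cases (0.8 to 1.9 percentage points of 40).
- k = 4: 0.64 to 1.48 cases (1.6 to 3.7 points).
- k = 8: 1.28 to 2.96 cases (3.2 to 7.4 points).

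These are upper-end illustrations. Section 3 gives that range as a prevalence from retrospective studies, with ARN defined in the setting of an INR above 3.0. Section 1 ties 37% to the patients at highest risk. A mid-study switch also leaves less than six months to observe.

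**3. Study-drug reading: the switcher is removed.** The withdrawal section then deletes everything, so valid on-drug months are lost.

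- With no cases, deleting 2, 4 or 8 switchers leaves 38, 36 or 32 participants, and the upper limit rises from 8.8% to 9.3%, 9.7% or 10.9%. This loss of precision is small.
- The greater problem is a deleted event. If there were 2 true on-drug cases and one of those participants was then switched, the result falls from 2/40 = 5.0% (0.6 to 16.9%) to 1/39 = 2.6% (0.1 to 13.5%). The event may itself have prompted the switch.

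Here the bias is downward, towards the hypothesis.

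**4. Would the data show a switch?** No planned follow-up item records the current anticoagulant. For an event, the treating physician's work-up is reported to the team and enters the database, so a switch may come to light, but no rule requires the work-up to state the drug. For an event-free switcher there is not even that source.

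**The case against.** The best reply is that, for this study's own participants, anticoagulation means the study drug. The inclusion criterion ties the word to rivaroxaban or apixaban, the objective concerns patients on those drugs, and the section on alternative treatments says patients are observed on treatment already begun. On that reading a switcher is censored and no warfarin case is counted. The physician's work-up might also attribute the injury to the new drug, and detailed on-drug windows often belong in a statistical analysis plan.

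Much of this stands. A reader might infer that the Protocol settles the matter, so that switchers remain and their later injury counts as factor Xa inhibitor ARN. The documents do not support that: no section says so, and the narrower reading is arguable. A reader might also infer that nothing in the database could reveal a switch. That is too strong for events, because work-up data are stored.

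The reply does not remove the problem, however. The narrower reading leads straight to the deletion rule, which discards on-drug data and on-drug events. The adherence criterion ("Participant is willing to comply with all aspects of the protocol, including adherence to medical therapy and follow-up visit") concerns willingness at entry and does not govern later switches. Nor can an analysis plan recover change dates that were not collected or records that were deleted.

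**Conclusion.** The point holds as a mismatch between the exit rule and the objective, with no sound outcome on either reading: possible upward bias if switchers stay in, possible downward bias if they are removed and their data deleted. It is not a misclassification that the Protocol prescribes.

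The size cannot be fixed from the document. It rests on an unstated switch rate and on the risk after a switch, and is nil if nobody switches. The amended wording is worth having because each single case is 2.5 percentage points of 40, the contrast of interest is with warfarin itself, and the correction is cheap.

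**What to change.** The changes concern analysis and data capture only, not treatment.

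- In Study Endpoints and in the first item of Withdrawal of Subjects, define time at risk for the primary endpoint as time on rivaroxaban or apixaban. It ends when the participant stops them or changes to a different anticoagulant. A change between the two stays in the pooled estimate.
- At each of the four scheduled draws, record the current anticoagulant and the date of any change.
- Amend the deletion rule in Withdrawal of Subjects so that data and events up to the change are kept. Without this, the first change contradicts it.
- List kidney injury first detected after the change separately, by the drug taken at the time and outside the primary count. The window should not run on to the next scheduled draw: after a switch just past month 3 that draw is at month 6, so nearly three months on another drug would be counted.

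The cost is one protocol amendment and one line on the visit form, with no extra visits. Switchers contribute less counted follow-up, and an on-drug event first detected after the switch would appear only in the separate listing.
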